1.2 Synopsis

National Co-ordinating Investigator

[name]
Jefe de Servicio de Oncología Médica
Hospital Clínico Universitario Lozano Blesa
[name]
[name]
e-mail: [contact]

Protocol Title:

A Phase IIIB, Single Arm Study, of Durvalumab in Combination with Platinum-Etoposide for Untreated Patients with Extensive-Stage Small Cell Lung Cancer reflecting Real World Clinical Practice in Spain (CANTABRICO)

A Phase IIIB Study in Untreated Patients with Extensive-Stage Small Cell Lung Cancer

Rationale:

Recent data indicate that in 2018 lung cancer has been the leading cause of death from tumors in Spain (22,153 deaths). Small-cell lung cancer (SCLC) represents approximately 13% of all newly diagnosed lung cancers (Puglisi et al 2010). SCLC is perhaps the most aggressive form of the disease. Extensive-stage disease (ES) was defined as any tumor that extended beyond the boundaries of a single radiation port and is identified in ~70% of patients with SCLC.

Four to six cycles of platinum based chemotherapy, etoposide in combination with either cisplatin or carboplatin has been the standard care (SoC) for patients with ES SCLC for the past 25 years (Pignon et al 1992, Roth et al 1992). Despite high initial response rates of up to 70% (Rossi et al 2012), it is estimated that 80% of patients with limited stage and almost all patients with ES SCLC will relapse or experience disease progression (Clark and Ihde 1998). Therefore prognosis for patients with SCLC in general and particular ES SCLC is poor; the reported 2-year survival is only 5% and 5 years survival rate is less than 2% (Rossi et al 2012).

The phase III, randomised, open-label CASPIAN study showed a statistically significant improvement in overall survival (primary study endpoint) with first-line durvalumab and etoposide plus either cisplatin or carboplatin (platinum–etoposide) versus platinum–etoposide alone in patients with ES-SCLC at a planned interim analysis.

Despite the positive results, there remains limited information about the effectiveness and safety of durvalumab plus platinum-etoposide in ECOG PS 2 patients, as well as in patients having received CRT as a definitive treatment for a limited stage (LS)-SCLC and with progressive and platinum-sensitive disease at least 6 months after treatment; there is also limited information in patients with some stable comorbidities, controlled autoimmune diseases, or even in those patients where the investigator can expect benefit from a prophylactic cranial irradiation. Therefore, there remains an unmet need for additional data to help support and inform the health-care decisions in the use of durvalumab in combination with platinum–etoposide as first-line treatment for unselected patients with ES-SCLC in real clinical practice.

In the treatment of lung cancer, it is important to both increase survival and palliate symptoms because disease symptoms have negative impacts on health-related quality of life (HRQoL) (Hyde and Hyde 1974; Hopwood and Stephens 1995; Sarna et al. 2004). In this study, the validated EORTC QLQ-C30 and EORTC QLQ-LC13 will be used to assess HRQoL, physical functioning, and symptom severity.

The present study will assess the safety and effectiveness of durvalumab plus platinum-etoposide in a real world ES-SCLC population until P&R approval of durvalumab in ES-SCLC based on CASPIAN results.

This trial will generate clinically relevant safety and efficacy data with durvalumab in combination with EP under conditions that reflect a real-world setting...

Objectives and Endpoints

Primary objective:	Endpoint/variable:
To describe safety profile of durvalumab in combination with platinum–etoposide as first-line treatment for patients with ES-SCLC	
Incidence of grade \geq 3 AEs
 
Incidence of imAE

Secondary objective:	Endpoint/variable:
To describe effectiveness of durvalumab in combination with platinum–etoposide as first-line treatment for patients with ES-SCLC.	
Progression Free Survival (PFS).
 
PFS rate at 6 months and at 1 year (PFS6, PFS12).
 
Objective Response Rate (ORR): using site investigator assessments according to RECIST 1.1.
 
Duration of Response (DoR).
 
DoR at 1 year (DoR12)
 
Time to Treatment Discontinuation (TTD).
 
Overall Survival (OS).
 
The OS rate at 6, 12 and 18 months.
 
Time to event endpoints measured as time from first Durvalumab dose.

To describe the impact of durvalumab in combination with platinum–etoposide as first-line treatment for patients with ES-SCLC on patients’ disease-related symptoms and Health Related Quality of Life (HRQoL) and (PROs).	
Changes in vital signs, physical findings, and clinical laboratory results during and following study treatment administration.
 
Change from baseline in European Organisation for Research and Treatment of Cancer Quality of Life Questionnaire Core 30 items (EORTC QLQ-C30).
 
Change from baseline in European Organisation for Research and Treatment of Cancer Quality of Life Questionnaire-Lung Cancer 13 (EORTC QLQ-LC13).

To describe health care resources use related to management of ES-SCLC patients treated with durvalumab in combination with platinum–etoposide as first-line treatment.	
Changes from baseline in PRO-CTCAE.
 
 - Number and length of hospitalizations - Number of visits to oncology service - Number of emergency visits - Number of outpatient visits - Number of imaging tests - Number of biopsy-related procedures - Treatment dose, duration, number of cycles

Objectives and Endpoints

Exploratory objective:	Endpoint/variable:
[REDACTED]	[REDACTED]
[REDACTED]	[REDACTED]

Overall design:

Phase IIIb, interventional, single arm, multicentre study to evaluate safety, effectiveness, use of resources and patient reporting outcomes in patients with ES-SCLC treated with durvalumab in combination with platinum–etoposide as first-line treatment in Spain.

Prophylactic cranial irradiation (PCI) is allowed in patients showing complete or partial responses after chemo-Durvalumab treatment under investigator criteria.

Study Period:

Estimated date of first patient enrolled: Q4 2020

Estimated date of last patient enrolled*: Q2 2021

Estimated date of last patient completed: Q2 2022

**Recruitment duration may be reduced or extended, until P&R approval of durvalumab in ES-SCLC based on CASPIAN results.*

Number of patients:

This is a safety study, and given the real-world setting, there is no formal predefined statistical hypothesis and no formal sample size calculation will be done.

A convenience sample size of approximately 85 patients was estimated based on the expected accrual potential during 6 months in 30 sites, although the recruitment duration may be reduced or extended, until P&R approval of durvalumab in Spain for ES-SCLC based on CASPIAN results, and the number of patients recruited could be higher. A maximum of 30% of recruited patients will have ECOG performance status of 2 at baseline.

Treatments and treatment duration:

Durvalumab will be concurrently administered with first-line chemotherapy (EP) on an every 3 week (q3w) schedule for 4 to 6 cycles, and will continue to be administered post-chemotherapy on an every 4 week (q4w) schedule until confirmed progressive disease (PD) or unacceptable toxicity.

Durvalumab + chemotherapy combination

- Durvalumab 1500 mg via IV infusion q3w concurrently with chemotherapy, starting on Week 0, for 4-6 cycles. Please note, if a patient's weight falls to 30 kg or below (≤ 30 kg), then the patient should receive weight-based dosing equivalent to 20 mg/kg of durvalumab after consultation between the Investigator and Study Physician, until the weight improves to above 30 kg (>30 kg), at which point the patient should start receiving the fixed dosing of durvalumab 1500 mg.
- EP: the dose of etoposide + carboplatin or cisplatin investigated will not exceed the product label dose for the given indication dose (etoposide [80 to 100 mg/m²] via IV infusion with either carboplatin [area under the curve (AUC) 5-6] via IV infusion or cisplatin [75 to 80 mg/m²] via IV infusion), starting on Week 0, for 4-6 cycles.

Durvalumab monotherapy

- Durvalumab 1500 mg via IV infusion q4w, starting 3 weeks after the last infusion of the combination, until confirmed progressive disease (PD) or unacceptable toxicity. Please note, if a patient's weight falls to 30 kg or below (≤ 30 kg), then the patient should receive weight-based dosing equivalent to 20 mg/kg of durvalumab q4w after consultation between Investigator and Study Physician, until the weight improves to above 30 kg (>30 kg), at which point the patient should start receiving the fixed dosing of durvalumab 1500 mg q4w.

Duration of treatment

Unless specific treatment discontinuation criteria are met, patients will continue therapy until clinical progression or confirmed radiological progression (defined in Appendix E).

Progression during treatment

During the treatment period, patients who are clinically stable at an initial RECIST 1.1-defined PD may continue to receive study treatment at the discretion of the Investigator and patient. A follow-up scan is to be collected after the initial RECIST 1.1-defined PD, preferably at the next (and no later than the next) scheduled imaging visit, and no less than 4 weeks after the prior assessment of PD and this scan is evaluated using the Confirmation of Radiological Progression criteria are outlined in Appendix E. If the subsequent scan does not confirm the immediate prior radiological PD, scanning should continue until the next RECIST 1.1-defined PD which in turn will require a subsequent scan evaluated using the Confirmation of Radiological Progression criteria outlined in Appendix E.

Follow up of patients post discontinuation of study drug

Patients who have discontinued treatment due to toxicity or symptomatic deterioration, clinical progression, or who have commenced subsequent anticancer therapy will be followed up with tumor assessments until RECIST 1.1-defined PD plus an additional follow-up scan or until death (whichever comes first) and followed for survival.

Survival

All patients in the study should be followed up for survival.

Statistical methods

All statistical analyses will be performed by AstraZeneca or its representatives (e.g. CRO).

A comprehensive statistical analysis plan (SAP) will be prepared and finalized within 3 months of the first enrolled patient, and any subsequent amendments will be documented, with final amendments completed prior to reporting of the data.

All analyses will be descriptive in nature. Categorical (e.g., gender) study measures will be reported using frequency and proportions and continuous measures (e.g., age) will be reported using mean, median, standard deviation and range. Additionally, Kaplan-Meier curves will be presented for time-to-event outcomes such as overall and progression free survival.

All analyses will be based on the intention to treat (ITT) population consisted of all enrolled patients who had received at least 1 dose of study drug (chemotherapy or Durvalumab). For the overall study population and for any subpopulation, estimated 95% CIs for various event rates will be calculated.

The incidence of common, or uncommon (<1%) serious adverse events will be estimated. Serious adverse events, grade 3/4 AEs, AE leading to death, AE leading to discontinuation, imAE and adverse events of special interest will be summarised by preferred term and incidence rates.

[figure not shown]
Baseline will be the last assessment of the variable under consideration prior to the intake of the first study drug (Durvalumab) dose.

Planned subgroup analyses of safety and effectiveness according to baseline characteristics include: ECOG status, gender, , presence of brain or liver metastases, smoking status, age of 65 years or older, and use of prophylactic cranial irradiation.

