4. STUDY DESIGN

4.1 Overall design

For an overview of the study design see Figure 1, Section 1.3. For details on treatments given during the study, see Section 6.1 Treatments Administered.

For details on what is included in the efficacy and safety endpoints, see Section 3 Objectives and Endpoints.

This is a Phase IIIb, interventional, single arm, multicentre study to evaluate safety, effectiveness, use of resources and patient reporting outcomes in patients with ES-SCLC treated with durvalumab in combination with platinum–etoposide as first-line treatment in Spain.

This study will include approximately 85 eligible patients at participating Spanish sites.

Durvalumab will be concurrently administered with first-line chemotherapy (EP) on an every 3 week (q3w) schedule for 4 to 6 cycles, and will continue to be administered as monotherapy post-chemotherapy on an every 4 week (q4w) schedule until confirmed progressive disease (PD) or unacceptable toxicity.

Prophylactic cranial irradiation (PCI) is allowed in patients showing complete or partial responses after the durvalumab + EP combination cycles, at the discretion of the investigator according to their local clinical practice.

Assessments will be conducted as indicated in Table 2 and Table 3.

Tumor assessments will be performed at Screening as baseline with follow-ups following local standard practice, but at least with a maximum interval of 12 weeks. It is recommended that on-study tumor assessments occur at Week 9 \pm 1 week from the date of inclusion for the first 12-18 weeks (during durvalumab + EP, relative to the C1D1), and then every 8 \pm 1 weeks until confirmed objective disease progression (please refer to Appendix E).

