6.4 Concomitant therapy

The Investigator must be informed as soon as possible about any medication taken from the time of screening until the end of the clinical treatment phase of the study including the follow up period following the last dose of study drug.

Any medication or vaccine including over-the-counter or prescription medicines, vitamins, and/or herbal supplements that the patient is receiving at the time of enrollment or receives during the study must be recorded along with:

- Reason for use
- Dates of administration including start and end dates
- Dosage information including dose, unit and frequency

Patients must be instructed not to take any medications, including over-the-counter products, without first consulting with the Investigator.

Restricted, prohibited, and permitted concomitant medications are described in the following tables. Refer also to the Dosing Modification and Toxicity Management Guidelines (see Section 8.4.5).

Table 6 Prohibited concomitant medications

Prohibited medication/class of drug:	Usage:
Any investigational anticancer therapy other than those under investigation in this study	Should not be given concomitantly whilst the patient is on study treatment
mAbs against CTLA-4, PD-1, or PD-L1 other than those under investigation in this study	Should not be given concomitantly whilst the patient is on study treatment
Any concurrent chemotherapy, radiotherapy, immunotherapy, or biologic or hormonal therapy for cancer treatment other than those under investigation in this study	Should not be given concomitantly whilst the patient is on study treatment. (Concurrent use of hormones for non-cancer-related conditions [eg, insulin for diabetes and hormone replacement therapy] is acceptable. Local treatment of isolated lesions, excluding target lesions, for palliative intent is acceptable [eg, by local surgery or radiotherapy]) PCI is allowed in patients showing complete or partial responses after chemo-durvalumab treatment under investigator criteria.
Live attenuated vaccines	Should not be given through 30 days after the last dose of IP

Prohibited medication/class of drug:	Usage:

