#### **EP**

- Platinum administered (Cisplatin; Carboplatin): The following data will be described for each category.
- Total dose administered (mg) (Continuous)
- Total dose programmed (mg/m^2 for Cisplatin / AUC for Carboplatin) (Continuous)
- Number and percentage of patients receiving 4 or more cycles of EP (Categorical)
- Number and percentage of patients receiving 5 or more cycles of EP (Categorical)
- Number and percentage of patients receiving 6 or more cycles of EP (Categorical)
- Duration of EP treatment in weeks (Continuous)
- Treatment interruption (Yes, No): If affirmative:
  - Number and percentage of patients with at least one treatment interruption
  - Reason for interruption (Categorical)
  - Total number of cycles interrupted and percentage regarding total cycles
- Dose delay (Yes, No): If affirmative:
  - Number and percentage of patients with at least one dose delay
  - Reason for delay (Categorical)
- Dose reduction (Yes, No): If affirmative:

- Number and percentage of patients with at least one dose reduction
- Reason for reduction (Categorical)
- Number and percentage of patients who received prophylactic cranial irradiation (PCI) in patients showing complete or partial responses after the durvalumab + EP combination cycles will be described. To calculate the number of patients receiving PCI, the information collected on concomitant study medication will be considered.

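### The synopsis lists use of prophylactic cranial irradiation as a baseline subgroup factor, but it is given after response to the combination, so outcome summaries by this factor tend to favour it even with no effect

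*Protocol*

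**What the plan says.** Protocol 1.2 Synopsis, Statistical methods, gives this definition: "Baseline will be the last assessment of the variable under consideration prior to the intake of the first study drug (Durvalumab) dose". It then states: "Planned subgroup analyses of safety and effectiveness according to baseline characteristics include: ECOG status", and the list closes with "smoking status, age of 65 years or older, and use of prophylactic cranial irradiation".

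The same synopsis, under Overall design, sets the condition for PCI: "Prophylactic cranial irradiation (PCI) is allowed in patients showing complete or partial responses after chemo-Durvalumab treatment under investigator criteria". Protocol 4.1 agrees that PCI "is allowed in patients showing complete or partial responses after the durvalumab + EP combination cycles". Table 6 in Protocol 6.4 and SAP 2.1 carry the same condition. Protocol 6.1.2.2 leaves PCI to the investigator under standard of care and does not mention response.

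PFS and OS are timed from the start of treatment (synopsis endpoints; Protocol 9.4; SAP 4.2.2.1). ORR is the percentage with CR or PR (Protocol 9.5.2.2; SAP 5.2.1).

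The subgroup lists in Protocol 9.5.1 and 9.5.2.2 and in SAP 5.1 and 5.2.1 do not contain PCI. In the SAP, PCI appears only as a descriptive number and percentage among responders (4.3.4.1, EP), with the source given as: "To calculate the number of patients receiving PCI, the information collected on concomitant study medication will be considered".

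**The concern.** A factor settled three to four months after the clock starts cannot be handled like age or sex. To be counted in the PCI group a patient must live long enough to receive it and, in most of the text, must have responded. The time before PCI is event-free by selection, yet it is credited to the PCI group. This is guarantee-time (immortal-time) bias, with selection on response added.

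The bias needs no hypothesis test to appear. The synopsis promises Kaplan-Meier curves for time-to-event outcomes and 95% intervals for event rates in any subpopulation, so a plain table of 6-month PFS by PCI would already carry it. A reader of such a table could credit PCI with an advantage that comes from how the groups were formed.

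Adverse event counts by PCI are affected too. PCI recipients have survived and usually been exposed for longer, and patients who died or stopped early are in the other group. The direction for safety cannot be fixed from the documents.

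**Working it through.** The documents give no figure for a PCI subgroup. Their only precision figures (Protocol 9.2, exact 95% intervals at n = 85) reproduce, apart from a rounding difference in a half-width: at 70% it is 10.1 points against the stated 10.0.

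**1. When PCI status is settled.** 4 cycles x 3 weeks = 12 weeks and 6 x 3 = 18 weeks. With 30.44 days per month, 12 x 7 / 30.44 = 2.76 months and 18 x 7 / 30.44 = 4.14 months. Baseline is before the first dose, so PCI is a post-baseline factor.

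**2. Events before PCI can start.** Assume exponential times with median m, so the share with an event by time t is 1 - 2^(-t/m).
- Deaths, m = 13.0 months (Protocol 2.3.1.2): 1 - 2^(-2.76/13) = 13.7% by week 12; 1 - 2^(-4.14/13) = 19.8% by week 18.
- Progressions, m = 4 to 6 months (Protocol 2.3.3, chemotherapy alone): 27-38% by week 12; 38-51% by week 18.

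Under the response condition all of these patients fall in the no-PCI group.

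**3. Effect on a purely descriptive table.** 6-month PFS for everyone is 2^(-6/4) = 35% to 2^(-6/6) = 50%. Among patients required only to be event-free at week 12 it is 2^(-3.24/4) = 57% to 2^(-3.24/6) = 69%. The gap of about 19-22 points arises with no PCI effect and no model.

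**4. Null simulation.** Taken from the documents: median OS 13 months, and median time to progression 5 months (midpoint of 4-6). Response is 60% or 70%; the documents say up to 70% (Protocol 2). Assumed, because the documents give no values: PCI to 20% or 40% of responders still alive and progression-free at week 12 or 18, PFS/OS correlation 0.7, censoring at 18 months. PCI has no effect. Hazard ratio of PCI versus no PCI, timed from first dose:

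| Prognostic value of response | PFS HR | OS HR |
|---|---|---|
| None | 0.52-0.64 | 0.41-0.57 |
| Responders have half the hazard | 0.43-0.56 | 0.32-0.44 |

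A second simulation built OS as PFS plus a post-progression time, with PCI at 3-4.5 months in 30-50% of progression-free responders. It gave 0.47-0.58 for PFS and 0.52-0.57 for OS. Every scenario favours PCI.

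As a gauge at trial size, about 1,000 simulated trials of 85 patients were run with 70% response, 30% uptake and PCI at week 12. The median HR was 0.63 (PFS) and 0.54 (OS), or 0.54 and 0.43 with prognostic response. A nominal p < 0.05 would occur in 19-43% of trials. Some fits did not converge, so these percentages are approximate.

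**5. ORR.** With the response condition applied, ORR is 100% with PCI and 52-68% without, purely from the grouping rule.

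**6. Does a landmark remove the bias?** Restrict to responders alive and progression-free at week 12 or 18 and restart the clock there. The null HR returns to 0.95-1.05 (PFS) and 0.96-1.03 (OS). Without the response restriction, and with responders at half the hazard, it stays at 0.74-0.88 (PFS) and 0.71-0.86 (OS).

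**7. Size of the landmark set.** 85 x response x 2^(-t/5):
- 70% response: 85 x 0.70 x 0.682 = 41 at week 12; 85 x 0.70 x 0.563 = 34 at week 18.
- 60% response: 35 and 29.

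At 30% uptake, the week-18 set with 70% response would hold about 10 PCI recipients.

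**The case against.** The strongest reply is that nobody has planned the biased comparison in operative text. The study is descriptive with no hypothesis. The Cox, log-rank and ORR subgroup wording in Protocol 9.5.2.2 and SAP 5.2.1 is attached to lists without PCI. Protocol 9.4 leaves the details of the analyses to the SAP, which only counts PCI recipients. All of that stands. A reader might infer that a PCI hazard ratio or test is pre-specified; the documents do not support that, and the rejection rates above only gauge the bias.

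It does not dispose of the point. The synopsis still calls the subgroup planned, nothing explains its absence elsewhere, and descriptive curves and event rates carry the same bias. The omission cannot be read as a deliberate restriction to baseline factors either, because SAP 5.2.1 adds the number of chemotherapy cycles, which is also fixed after baseline.

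Three other stronger readings fail:
- **That PCI benefit is the stated evidence gap.** The rationale (synopsis and Protocol 2.1) names limited information on durvalumab plus platinum-etoposide in patients for whom the investigator expects benefit from PCI. Whether PCI works is not the question posed.
- **That the PCI date may go uncollected.** Protocol 6.4 asks for start and end dates of concomitant treatment, its Table 6 names PCI, and the SAP uses that source. The eCRF is not among the documents, so a gap cannot be shown.
- **That ORR in the PCI group must be exactly 100%.** Protocol 6.1.2.2 lacks the response condition, and PCI follows the investigator's judgement while ORR is derived by program from RECIST data. Close to 100% is the supportable statement.

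**Conclusion.** The point holds. PCI use is a post-baseline factor listed under baseline characteristics, and any effectiveness split by it, timed from first treatment, tends to favour PCI when there is no effect. Illustrative null hazard ratios are about 0.43-0.64 for PFS and 0.32-0.57 for OS. ORR by PCI is uninformative, and adverse event counts by PCI are distorted by differing survival and exposure.

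The direction follows from the definitions. The size depends on assumed uptake, PFS/OS dependence and prognostic value of response, and on a progression median from chemotherapy alone. A single trial of about 85 patients need not show a large difference. The documents also disagree: the synopsis plans this subgroup, while Protocol 9.5 and the SAP lists leave it out without comment.

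**What to change.** Delete the PCI item from the baseline-subgroup list in the synopsis so that it agrees with Protocol 9.5 and the SAP, and keep the descriptive PCI count in SAP 4.3.4.1. This is a one-line change. Protocol 6.1.2.2 should also be reconciled with the synopsis, 4.1, Table 6 and SAP 2.1 on whether response is a condition for PCI. Which wording is right is not a statistical matter.

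If an outcome result by PCI is wanted, specify it in SAP 5.2.1 as exploratory:
- restrict to patients alive, progression-free and in CR or PR at a fixed time after the combination, restart the clock there, and group by PCI received by then; or
- fit PCI as a time-dependent covariate within responders.

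Give no ORR by PCI.

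The cost is a small set, roughly 30-40 of 85 patients under the illustrative assumptions, and wide intervals. A fixed landmark also fits the 4-6 cycle range imperfectly, because PCI given after it counts as no PCI; the time-dependent form avoids that.
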